1. BACKGROUND AND RATIONALE

1.1. General Introduction

Stroke is a significant cause of disability and the overall fourth-highest cause of disease burden in Singapore. Crude incidence of stroke in Singapore has increased from 187.9 (2008) to 196.7 (2012) per 100 000 population¹. The prevalence of stroke events is expected to increase worldwide due to the increase in the population aged above 65 years old.

The mean annual direct medical cost of stroke in Singapore is S\$12473.7, of which 93.6% of the cost comes from inpatient hospitalization. This amount is substantially higher than other prevalent inpatient hospitalization and other Asian countries. It does not account for outpatient rehabilitation services and direct non-medical cost such as out-of-pocket expenses and loss of work. It is important to bear in mind that the economic impact of stroke goes beyond acute care; it extends to costly prolonged institutional chronic care and rehabilitation. Therefore, it is important to maximize recovery after stroke to reduce disability and burden of care on individuals, within Singapore and worldwide.

Upper limb (UL) recovery after stroke has been found to be limited. Singapore data has revealed that less than one-third of the stroke patients regained UL dexterity one year after their strokes. The remaining two-third of the stroke population had to live and cope with enormous losses associated with their UL impairments for the rest of their lives. In view of the importance of hand dexterity for the performance of daily functional tasks, rehabilitation efforts should be channelled into facilitating UL recovery after stroke.

The effects of rehabilitation on UL recovery after stroke appear to be more pronounced in the first six months post-stroke. It appears that there might be an optimal time window for gaining favourable rehabilitation outcome post-stroke.

During this optimal time window, the use and the practice of the affected UL influence neuroplasticity and facilitate UL recovery after stroke. On the other hand, the lack of affected UL use leads to the “learned non-use” phenomenon and the development of compensatory strategies (i.e. overuse of non-affected UL), which interfere and hinder the neuroplasticity process for recovery. Therefore, the use and practice of the affected UL at the early phase post-stroke is crucial and important.

This can also be seen from the results of early intervention studies. These studies have shown that additional early UL practice resulted in better UL functional outcomes when compared with conventional/ traditional therapy alone. For patients with less severe UL impairment, early increased UL practice appeared to have pushed them to a higher level of UL functional outcomes. This higher level of UL functional outcomes was maintained even up to 9 to 12months post-stroke.

Gap in the Knowledge of Optimal Effective Early UL Practice

For early increased UL practice, “more” might not necessary mean better as seen in the early constrained-induced movement therapy (CIMT) study results. In these studies, lower intensity CIMT intervention was found to be more beneficial when compared with higher intensity CIMT intervention during the early post-stroke phase. A possible explanation for this result was that the subjects in the higher intensity group might have experienced fatigue. In addition, the requirement of the higher intensity UL practice might have resulted in “blocked” practice schedule rather than the desired “distributed” practice schedule throughout the day. Distributed learning schedules have been found to lead to better motor task learning and performance. It appeared that early increased UL practice after stroke might be more effective if it is incorporated into affected UL practice and use distributed throughout the day rather than concentrating all the intensive UL practice within one therapy session in a day.

To date, there are still gaps in the knowledge of the optimal dosage intensity, optimal timeline to commence

UL practice and optimal effective mode of early UL practice after stroke.

Gap in the Knowledge of Neuroplasticity During Early Post-Stroke

To fill the gaps in knowledge of early UL practice, the understanding of the neuro-biological mechanism of recovery after stroke might be the key to answer these questions. In fact, it has been found that early increased UL practice does not necessarily mean better outcomes in neuroplasticity. In studies of rats, it was found that forced overuse of the affected limb 7 days (by casting the unaffected limb) after an induced stroke actually caused an expansion of the neural injury and interference in the restoration of affected limb function. Although it is always important to interpret results of animal studies with caution, the results show that there is a need for a greater understanding of the neuroplasticity mechanism behind early UL increased practice, otherwise we might possibly do more harm than good to stroke patients.

There is still a lack of studies investigating the neuroplastic reorganisation of increased UL practice during early post-stroke. Only one study has been found, thus far, on investigating the effect of early increased UL practice on neuroplasticity after stroke in humans. In this recent study by Hubbard et al, fMRI (functional magnetic resonance imaging) showed that stroke patients in the early increased training group showed increased activation in ipsilesional anterior cingulate and supplementary motor areas, and reduced activation in contralateral cerebellum, when compared to the standard care group. The increased activation of ipsilesional anterior cingulate and supplementary motor areas in the early increased training group was associated with early motor learning and attention, and the reduction in the activation of the contralateral cerebellum was interpreted as constituting better recovery in stroke patients.

Most studies investigated the effect of additional UL practice on neuroplasticity on patients of more than 3-months post-stroke and patients of chronic stroke (>6-months post-stroke). These studies did not include control groups of stroke patients without UL additional practice to compare their outcomes. If there was a control group in these studies, the controls were normal healthy subjects.

The results of these studies showed that for stroke patients who had undergone a period of increased UL practice, there was a trend towards a decreased activation of contralateral motor area and supplementary motor areas and an increased activation in the ipsilesional motor area. This trend was approaching towards the activation pattern of normal healthy controls in their studies. However for stroke patients who had lower UL baseline motor capability, the gain in UL recovery after UL practice corresponded to an increase in both the ipsilesional and contralateral motor areas and supplementary motor areas. The neural reorganisation after increased UL practice after stroke varied across different individuals.

The complexity of neural reorganisation and the lack of studies on early increased UL practice on the neuroplasticity mechanism after stroke cause this important scientific area to be poorly understood. The understanding of this scientific gap is important because most rehabilitations occur early post-stroke and it is during this period that UL training can interact to support spontaneous recovery for optimal functional outcomes for patients.

Importance of Identification of Potential Imaging Biomarkers for Recovery

Another key to understanding the neurobiological mechanism of recovery is to identify potential biomarkers for recovery at early post-stroke and its interaction with UL practice. In a study by Marshall et al, it showed a correlation between the results of early task-related fMRI with the motor recovery. Marshall et al suggested that the recovery related activation pattern justified the investigation on early intervention to enhance the recovery process. In a study by Yin et al, it was reported that a biomarker can potentially be identified for UL recovery after stroke using volume-based measurement and diffusion tensor imaging (DTI) based FA (Fractional Anisotropy) analysis.

In another study, Bylow used transcranial magnetic stimulation (TMS) and diffusion weighted image (DWI) and linear regression to predict the increase of UL Fugl-Meyer (FM) score with standardized and variable dosage of therapy in his study. The study showed that UL recovery could be predicted by presence of motor evoked potentials (MEP), FA analysis of the corticospinal tract but was insensitive to the dosage of UL practice. Deeper analysis of the study revealed that the variable therapy dosage which was defined as duration of time was not controlled in this study. To draw conclusion that therapy dose does not affect UL recovery might be premature. However, this showed that it is important to consider the interaction of both the neurobiology conditions and UL training in post-stroke recovery.

A potential biomarker to investigate in this study will be FA of the corticospinal tract and its interaction with increased UL practice during early post-stroke. FA of the corticospinal tract at early post-stroke has been found to correlate to later stage UL recovery. Interestingly, FA of the corticospinal tract has also been shown to increase significantly after training. Another potential biomarker to investigate in this study will be resting state fMRI, based on a previous A*STAR study which showed that individual gain in FM scores over 12 weeks could be predicted from the resting state fMRI.

Loss of Opportune Time During Early Post-Stroke To Influence Neuroplasticity

A recent systematic review of stroke patients in hospitals has revealed that the mean duration of UL activity training during a physiotherapy (PT) session was 4.1 minutes to 5.7 minutes and 17 minutes during an occupational therapy (OT) session during the acute phase. The duration and repetitions in each UL training session in clinical practice are far below what are required for to effect a cortical re-organization in motor skill learning. With further reduction in manpower in healthcare due to rising healthcare needs, implies that employing more therapist manpower to increase current UL practice after stroke will be even more challenging.

It has been found that stroke patients spent most of their time in the hospital ward being inactive. Studies have shown that the use and practice of affected UL was also minimal in the ward. Bernhardt et al (2007) found that stroke patients only used their affected UL 1% out of the activities of the day in the ward. The time during which the stroke patients spend in the ward is an opportune time for them to increase their affected UL practice and use. It also captures the optimal time window for neuroplasticity, and thus should be fully utilised and not be wasted.

The findings mentioned above showed that implementing therapy to increase UL practice in real clinical world is a challenge. The answers to the questions of neuroplasticity of early UL practice early post-stroke will only be meaningful if we can develop innovative ways to facilitate affected UL practice throughout the day in the ward to achieve the desired neuroplasticity for optimal recovery after stroke, even with reduced manpower. Hence, the purpose of this study is to develop and evaluate a new and innovative way of enhancing therapy to increase UL practice early post-stroke in the ward.

Background on Preliminary Data/ Results

Patients can be empowered to take ownership of their practice and recovery. This can be seen in a multi-site single blinded randomized controlled trial of GRASP (Graded Repetitive Arm Supplementary Program). GRASP is a self-administered graded program that incorporate additional complementary UL practice in the ward (on top of regular therapy sessions) by the patients without the direct involvement of therapists during practice. This is made feasible by giving stroke patients and their caregiver instruction booklets (based on the level of the affected UL function) and teaching them on the self-administered exercises found in the booklet. This is followed by regular and consistent reviews by therapists to check and progress the exercises. The result of this trial showed that patients in GRASP group achieved better UL outcomes post treatment than the control. In addition, the gains in the GRASP group were sustained 5 months after the program. The program has also utilized an important source of manpower – patient and their caregiver, which has often been underutilized or sometimes even neglected.

However, GRASP does not include the component of affected UL daily functional use. Affected UL daily functional use is important because from clinical experience, stroke patients often confine the practice of their affected UL to just during therapy sessions, as most of them do not know how to use their affected UL after stroke, especially for those with lower UL motor function. Reduced affected UL use perpetuates even to chronic phase as they have not learned how to incorporate the use of their affected UL in daily life, resulting in the phenomenon of “learned non-use”.

In this new proposed program, ***Self-empowered Upper Limb Repetitive Engagement (SURE)*** program, specific instructions and guidance according to the level of their affected UL motor function will be given to guide and increase affected UL daily functional use in stroke patients in the ward. In addition, prescribed specific exercise according to the level of their affected UL motor function will also be given and guided to facilitate patients to exercise by themselves in the ward. The activity of the affected UL will be objectively and accurately monitored, reviewed and feedback to the patients to facilitate affected UL use and practice using accelerometers. Accelerometry has been found to be valid and reliable in the measurement of UL use in

stroke patients.

To date, there is no therapy program that has specifically and systematically been introduced in Singapore to facilitate UL practice and use of the stroke patients in the ward. Taking into consideration the challenge of increased UL practice during early post-stroke in the real clinical world, it is, therefore, important to investigate the feasibility and effectiveness of **SURE** program and the potential imaging biomarkers to optimize the neuro-rehab

1.2. Rationale and justification for the Study

a. Rationale for the Study Purpose

The recovery of affected UL is important both functionally and psychologically for the stroke patients. Less than one-third of the stroke population has return of dexterity of affected UL after stroke. More can be and should be done to facilitate recovery of affected UL after stroke.

Early increase UL practice has been shown to improve UL recovery. However, there are still gaps in the knowledge of optimal dosage, optimal timeline of commencement and efficacious mode of UL practice. The understanding of neuroplasticity and identification of potential imaging biomarkers at early post-stroke stage might be the key to answer these questions in early UL practice.

Stroke patients can be empowered to take ownership of their practice and recovery. The practice of affected UL in the ward and the patients/ their caregivers are underutilized resources that can be tapped into to increase UL practice. **SURE** program is a new and innovative program that empower stroke patients to increase UL practice in the ward early post-stroke to influence neuroplasticity and improve functional outcomes.

Therefore, the aims of this study are:

- 1) To investigate the feasibility and effectiveness of **SURE** program to increase UL practice in the ward and improve UL functional outcomes after stroke. To correlate the imaging biomarkers with the neuro-recovery outcomes under **SURE** and controlled program.
- 2) To investigate the neuroplasticity in the brain through multiple neuro-imaging analysis (fMRI/MRI/DTI), with the goal to develop imaging biomarkers for image-guided neuro-rehabilitation framework so as to optimize early UL practice after stroke.

b. Rationale for Doses Selected

The subjects will perform the self-exercises for 60 minutes (3x 10-20minutes) and functional tasks (as and when is required in the daily function) per day for 6 days per week in the ward throughout the 4 weeks intervention period. These exercises are performed in addition to daily therapy. Additional period of self exercises and affected UL's functional use are performed in the ward to increase the dosage of affected UL activity as studies have found that amount of affected UL activity during therapy session are limited.

c. Rationale for Study Population

20 eligible stroke subjects with positive motor evoked potential (MEP +ve) and with severe to moderate UL paresis (ULFM score below or equal to 50) admitted to TTSRHC will be selected. Subjects with severe and moderate UL paresis are selected because based on clinical observation subjects with this level severity require intensive UL practice to improve their UL functions, while subjects with mild paresis do not require such high intensity of UL practice for significant improvement. Investigation of motor evoked potential on extensor carpi radialis on the affected hand will be performed on stroke patients at NUH using a single Magstim 200 to prognosticate recovery. Subjects with MEP +ve will be selected to ensure that all the subjects chosen in this study have intact ipsilesional cortical spinal tract function to make comparison of UL

recovery more consistent.

d. Rationale for Study Design

Randomized blinded controlled trial study design has been selected for this study to investigate whether if **SURE** program improves UL functional outcome and influences neuroplasticity positively to optimize UL recovery after stroke. This study design is chosen to prevent any bias in the assessment of outcomes.

2. HYPOTHESIS AND OBJECTIVES

2.1. Hypothesis

1. **SURE** program increases UL practice in the ward and improves UL functional outcomes post-stroke
2. Increased UL practice early post-stroke period influences neuroplasticity positively to optimize UL recovery
3. Imaging biomarkers are associated with rehab-methods and recovery of UL post-stroke

2.2. Primary Objectives

To investigate the effectiveness of SURE program to increase UL practice in the ward and improve UL functional outcomes after stroke. To correlate the imaging biomarkers with the neuro-recovery outcomes under SURE and controlled program.

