3.3. Inclusion Criteria

All patient subjects have to fit in the following Inclusion criteria to be included in the study: diagnosis of stroke due to infarct resulting in UL hemiparesis (with confirmation from MRI and Computed axial tomography (CT) scans); and admitted within first 21days post-stroke in TTSHRC with Montreal Cognitive Assessment (MoCA) score ≥ 19 . In addition, stroke subjects with positive motor evoked potential (MEP +ve) and with severe to moderate UL paresis (Upper Limb Fugl Meyer (ULFM) score below or equal to 50) admitted to TTSHRC will be selected. Subjects with severe and moderate UL paresis are selected because based on clinical observation subjects with this level severity require intensive UL practice to improve their UL functions, while subjects with mild paresis do not require such high intensity of UL practice for significant improvement. Investigation of motor evoked potential on extensor carpi radialis on the affected hand will be performed in NUH on stroke patients using a single Magstim 200 to prognosticate recovery. Subjects with MEP +ve will be selected to ensure that all the subjects chosen in this study have intact ipsilesional cortical spinal tract function to make comparison of UL recovery more consistent.

All normal healthy subjects aged 21 years old and above who are able to give informed consent and follow commands will be recruited.

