5. STUDY DESIGN

Experimental procedure

The subjects will be randomly assigned to a control (N=10) and experimental group (N=10).

Experimental Group

The experimental group will receive one **SURE** program booklet with specific instructions and pictorial illustrations of each exercise and functional use according to their affected ULFM score. There are 3 booklets available (Level 1A for patients with affected ULFM score from 0 to 10; Level 1B for patients with affected

ULFM score from 11 to 22; Level 2 for patients with affected ULM score from 23 to 50). Each **SURE** program booklet consists of stretching exercises, strengthening exercises and performance of simple motor tasks such as reaching, picking up cubes etc. Each exercise will be graded and progressed according to the subjects' affected UL capability by the Clinical Principal Investigator (CPI) who is an experienced principal physiotherapist. The **SURE** program booklet also consists of selected motor tasks to be performed by the subjects using their affected UL. Functional activities such as subjects will be using their affected UL to wipe their faces; wiping the table after eating; applying lotion by the affected hand along the unaffected arm and legs after shower; drinking water from cup/ bottle; lifting and placing affected hand on table top; etc. Each functional motor task will be selected, graded and progressed by the PI according to the subjects' affected UL motor capability during the reviews. The subjects will be taught how to perform the exercises and functional tasks during the first session. The performance of the exercises and functional motor tasks will be reviewed by the CPI three times per week for the first 2 weeks, two times for the third week and one time for the fourth week of intervention period.

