11. SAMPLE SIZE AND STATISTICAL METHODS

11.1. Determination of Sample Size

Since this study is a pilot exploratory trial, results of individual subjects from each group will be analysed in

detail to determine the difference in brain neuroplasticity between the control and experimental groups. N=10 from each group is chosen because it is deemed feasible to recruit stroke patients who will be willing to participate in this study clinically in the period of 2 years (the time period of the funding).

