11.2. Statistical and Analytical Plans

a. Study Statistical Analysis

Statistical analysis will be performed using STATA version 10.0 for Windows (StataCorp, TX, USA). Descriptive statistics will be used to describe subjects' demographics in each group.

Analysis of UL Functional Outcome

Wilcoxon signed-ranked tests will be used at each time points (pre, 2 weeks after start of intervention, post, 1month post-intervention, 3months post-intervention) to compare UL functional outcomes between the experimental and control groups. The significance level for all statistical tests will be set at $p<0.05$ levels. All data will be analysed by intention to treat.

Analysis of feasibility of accelerometers to measure affected UL use

Analysis of the compliance rate and responses from the questionnaire will be used to determine the feasibility and acceptance of using accelerometers to measure affected UL use after stroke.

Analysis of SURE Program's feasibility

Wilcoxon signed-rank test will also be used to compare outcomes of pain, fatigue and spasticity pre-and post-intervention period. The differences in the duration of affected UL use per day and the ratio of affected UL use/ non-affected UL use between the experimental group and control group (from the accelerometer recordings), the rate of compliance, the proportion of subjects who successfully complete the whole training, and the dropout rate will be calculated to assess the feasibility of **SURE Program**.

Analysis of fMRI investigation

Comparison of activation in primary motor cortex, secondary motor cortex and cerebellar hemisphere for bilateral sides will be done by comparing mean percentage signal change (%SC), absolute voxel counts (VC) and changes in geometric centers of these areas on both sides¹⁷. In addition, a laterality index (LI) will also be calculated to determine the relative cortical activity. Asymmetry has been found to restore to normal (L=1.0) when the affected hand movement improved after rehabilitation⁴¹.

Analysis of resting state fMRI/DTI

Functional connectivity and tract integrity^{32,38} will be studied by FSL with the normalization method^{39,40}. The secondary degeneration of the brain in the remote region to the primary lesion will also be studied for the sub-groups of subjects with less motor recovery³⁰.

MRS analysis

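### The biomarker objective, a correlation of imaging with recovery under each program, cannot separate a biomarker's own information from baseline upper-limb impairment

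*Protocol*

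**What the plan says.** Protocol section 2.2 sets the biomarker question inside the primary objective: "To correlate the imaging biomarkers with the neuro-recovery outcomes under SURE and controlled program". The linked hypothesis in section 2.1 is a bare association: "Imaging biomarkers are associated with rehab-methods and recovery of UL post-stroke". Section 2.3 gives the purpose, which is to develop biomarkers for image-guided rehabilitation.

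Patients enter "with severe to moderate UL paresis (Upper Limb Fugl Meyer (ULFM) score below or equal to 50". The booklet levels in section 5 start at zero ("Level 1A for patients with affected ULFM score from 0 to 10"), so baseline ULFM may run from 0 to 50. Section 6 makes ULFM a primary outcome as well, so baseline and outcome can share one scale.

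Section 1.1 supports FA with an association that mentions no baseline severity: "FA of the corticospinal tract at early post-stroke has been found to correlate to later stage UL recovery". It names resting-state fMRI as the second candidate.

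Section 11.1 fixes the size on feasibility ("N=10 from each group is chosen because it is deemed feasible to recruit stroke patients"). Section 11.2 applies p<0.05 to every test ("The significance level for all statistical tests will be set at"). It describes analyses of the imaging data, but none that relates a biomarker to recovery.

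**The concern.** A scan can guide rehabilitation only if it says something that the ULFM score, already taken at the bedside, does not. A patient with a mild deficit may have both better tract integrity and a better later score. Imaging and outcome then correlate even if imaging carries no information of its own. The objective as worded asks for that correlation, so an analysis that follows it faithfully leaves the useful question unanswered. Splitting it by program leaves 10 patients in each, too few for a precise estimate and no basis for comparing programs.

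**Working it through.** The protocol has no power or correlation figure to reproduce; 10 per group is a feasibility choice.

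**Inputs from the protocol.** n = 10 per program, 20 in total; significance level 0.05 (two-sided assumed); baseline ULFM 0 to 50.

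**Inputs assumed.** Correlation *a* between biomarker and baseline ULFM, 0.4 to 0.7; correlation *b* between baseline and follow-up ULFM, 0.7 to 0.8; normal variables.

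**Model in which the biomarker adds nothing.** With standardised baseline B, let X = aB + √(1−a²)·e₁ be the biomarker and Y = bB + √(1−b²)·e₂ the follow-up score, with independent errors. Then corr(X, Y) = ab, and the partial correlation given B is 0.

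**Critical values.** |r| = t/√(df + t²).
- Plain, n = 10 (df 8): 2.306/√(8 + 5.318) = 0.632.
- Plain, n = 20 (df 18): 2.101/√(18 + 4.414) = 0.444.
- Adjusted for baseline: 0.666 (n = 10, df 7) and 0.456 (n = 20, df 17).
- Adjusted for baseline and group, n = 20 (df 16): 2.120/√(16 + 4.494) = 0.468.

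**Simulated share of analyses with p<0.05** (100,000 per setting; separate runs agree within about one percentage point):

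| a | b | ab | plain, n = 10 | plain, n = 20 | adjusted for baseline |
|---|---|---|---|---|---|
| 0.4 | 0.7 | 0.28 | 12% | 22–23% | 5% |
| 0.4 | 0.8 | 0.32 | 14% | 28% | 5% |
| 0.6 | 0.7 | 0.42 | 23% | 47% | 5% |
| 0.6 | 0.8 | 0.48 | 30% | 60% | 5% |
| 0.7 | 0.7 | 0.49 | 31% | 62% | 5% |
| 0.7 | 0.8 | 0.56 | 42% | 76–77% | 5% |

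The n = 10 column matches the objective as worded; the n = 20 column is a pooled correlation.

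**Weaker links.** With a = b = 0.3 the plain rates are 5.7% (n = 10) and 6.6% (n = 20). With a = b = 0.5 they are 10.6% and 18.8%.

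**Recovery as gain.** With equal variances, corr(X, Y − B) = −a(1−b)/√(2(1−b)) = −a√((1−b)/2). This runs from −0.4·√0.10 = −0.13 to −0.7·√0.15 = −0.27. The rate is 7% at (0.4, 0.7) with n = 10 and about 16% at (0.7, 0.8) with n = 20. Over the whole grid it is 6–12% at n = 10 and 8–21% at n = 20. Once baseline is in the model, gain and follow-up score give the same biomarker coefficient and test, so adjustment also removes dependence on this choice.

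**Precision in one program.** For an observed r = 0.5 with n = 10: atanh(0.5) = 0.549, half-width 1.96/√7 = 0.741, so the 95% interval is −0.19 to 0.86.

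**Reading two programs side by side.** If the true correlation is the same in both, each reaches significance with probability *q*, and exactly one does with probability 2q(1−q). For a true r of 0.4, q = 0.21, giving 2 × 0.21 × 0.79 = 33%. For 0.6, q = 0.49, giving 50%.

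**The case against.** An objective is not an analysis specification. Section 2.2 names no coefficient, time point, definition of recovery or decision rule, and covariates for an exploratory association are often left to a statistical analysis plan, which is not shown. This stands in part: the silence of section 11.2 is not itself the defect. The question the objective asks is, because a later plan that follows its wording would inherit the limit.

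Three stronger readings are tempting, and the protocol does not support them.

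- **That the trial would produce false positives.** Hypothesis 3 claims only an association, and one that runs through severity is a true association. The percentages are false-positive rates only for the question of added information.
- **That the protocol's background shows baseline severity driving the two candidate biomarkers.** The sentence beginning "However for stroke patients who had lower UL baseline motor capability" concerns activation changes that accompany gains after practice, and section 1.1 describes most of that evidence as coming from patients more than three months after stroke. It says nothing on baseline FA or resting-state fMRI. That link is plausible but assumed here.
- **That the protocol plans to claim a biomarker works in one program and not the other.** No such rule is written. The side-by-side calculation is a reason to rule the reading out in advance, not evidence that it is planned.

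The pilot label excuses imprecision. It does not make an unadjusted correlation informative about added value.

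**Conclusion.** The point holds as a limit on what the stated objective can show: a correlation of imaging with recovery under each program cannot distinguish a biomarker from a proxy for baseline ULFM, and so cannot serve the aim in section 2.3. Under the assumed links, a measure with no added information would be significant against follow-up ULFM in about 12–42% of within-program analyses and 23–76% of pooled ones, against 5% with adjustment. The excess is much smaller, and the correlation negative, if recovery is gain; it nearly vanishes if both links are about 0.3. Every one of these correlations is an assumption. Selecting patients with a positive motor evoked potential narrows tract status but leaves the ULFM entry range at 0 to 50, so it does not settle the matter. The change is worth making because the baseline score is already collected.

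**What to change.** Restate the biomarker part of section 2.2 as the association of pre-intervention imaging with follow-up ULFM given baseline ULFM, for the two candidates in section 1.1 (corticospinal FA and resting-state fMRI). In section 11.2, specify one regression per biomarker on all 20 patients, with follow-up ULFM at a named visit as the outcome and baseline ULFM, group and the biomarker as terms. Report the biomarker coefficient as an exploratory estimate with its confidence interval. If the programs are to be compared, add a group-by-biomarker interaction as an estimate with interval only, and state that no comparison will be drawn from separate within-program p-values.

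The cost is a paragraph of text, with no new data or visits. Two extra model terms raise the critical |r| at n = 20 from 0.444 to 0.468 and widen the intervals somewhat; an interaction costs one more degree of freedom. Adjustment does not cure the imprecision of 20 patients. It also does not cover the planned analyses of change in imaging over time, which remain a separate question.
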